### **8.2. Name and description of intervention and standard care**

- Radioisotope Technetium^99 nanocolloid, 20 MBq
- Patent Blue dye 2.5%
- Indocyanine green (ICG) 0.5%

### **8.3. Concomitant medication**

Details of concomitant medications related to participants' breast cancer only will be recorded on the trial Case Report Form.

### **8.4. Trial restrictions**

All concomitant medications, including COVID-19 vaccine, will be allowed as per standard care. There will be no specific trial restrictions.

### **8.5. Assessment of compliance with treatment**

The time from incision to completion of SLN removal and use of tracers will be recorded in the CRF.

## 8.6. Pharmacovigilance

As the tracers in this trial are used in standard practice no adverse events will be collected for the trial. The safety profiles of the tracers are well known.

The formation of seromas, evidence of cutaneous staining and any other adverse reactions (AR) to the tracers will be recorded as outcomes and not recorded or reported as adverse events.

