ICG is a less expensive tracer than radioisotope although initial capital equipment costs (PDE camera) are higher. Nonetheless, in the longer-term use of ICG is likely to be more cost-effective than radioisotope taking account cost of the radioisotope injection per patient. Moreover, in a COVID-19 environment, additional visits to the nuclear medicine department can be avoided with use of ICG, whether this is on the day of surgery or before. The eventual use of ICG in place of radioisotope has the potential benefits of avoiding radioactive materials and problems of waste disposal and monitoring. Dispensing with the requirements for radioisotope facilities and mandatory licensing could save the NHS between £100 and £200 per patient. It is also important to stress that this is just for the cost of the radiocolloid injection. In addition to potential cost savings from avoiding necessity of a nuclear medicine facility, there are logistical advantages relating to booking and organising appointments for radiocolloid injection whether this be the day before or same day as surgery.

It is hypothesized that fluorescence mapping can provide at least equivalent sentinel detection rates but offer the opportunity for avoiding blue dye and eventually lead to improved cost-effectiveness if radioisotope is eventually abandoned for routine SLN biopsy. Abolition of blue dye with its associated risk of anaphylactic reaction (1-3%), skin tattooing and non-licensed use will be notable benefits of ICG. Of note, in a UK-Turkish study blue discoloration persisted at the injection site after 12, 24, and > 36 months in 36.5, 23.6, and 8.6% of the patients respectively.

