### 3.6. Table of endpoints/outcomes

Objectives	Outcome Measures	Timepoint(s) of evaluation of this outcome measure (if applicable)
Primary Objective To determine the sensitivity of fluorescence imaging alone for SLN identification compared with a combination of ICG and a standard tracer (blue dye or radioisotope)	Percentage of patients with successful identification of the SLN using ICG alone or combined with a standard tracer, stratified by cohort	At the time of SLN biopsy
Secondary Objectives Procedural node positivity rates	Proportion of SLN biopsy cases with tumour deposits in at least one node (including macrometastases, micrometastases and isolated tumour cells)	Post-surgery, when histopathology results are available
Adverse events from SLN biopsy	Seroma formation Cutaneous staining Other adverse reactions to tracers	2 weeks and 3 months

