## 2 weeks post biopsy

- Record adverse skin reactions i.e seroma formation and cutaneous staining

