## Follow-up phone call

- Record self-reported skin reactions

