### **9.5. Procedure(s) to account for missing or spurious data**

As patients are under the care of the surgeons and nodes are extracted during surgery, it is not expected that missing data will occur. Data will be examined for missing data, but no sensitivity analysis accounting for missing data will be performed.

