15.4. Appendix 4 – Schedule of Procedures

	Visit 1 Screening	Visit 2 Cambridge only Consent	Visit 3 Tayside only Baseline	Visit 4 Follow-up	Visit 5 Follow-up	As results are available
Type of Visit	Routine pre-biopsy visit	RN phone call	Routine biopsy visit	Routine visit	RN Phone call	
Timeline	Day -21 to 0	Day -20 to 0	Day 1	2 weeks (+/- 5 days)	3 months (+/- 7 days)	
Eligibility	X					
Provide PIS	X					
Informed Consent		X	X (Tayside only)			
Record Medical History			X			
Record Concomitant Medications			X	X	X	
Inclusion/exclusion		X	X (Tayside only)			
Randomisation		X	X (Tayside only)			
Record results of physical examination			X			
Record seroma formation and cutaneous staining				X	X	
Staining characteristics of SLN						X

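### Tracer reactions are a compared outcome, but the protocol sets no recording point on the day of injection and itemises only seroma, staining and skin reactions

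*Protocol*

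**What the plan says.** Five parts of the Protocol bear on this outcome.

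- **Definition.** The endpoint table in section 3.6 lists seroma, cutaneous staining and "Other adverse reactions to tracers", with evaluation at "2 weeks and 3 months". The Trial Summary names only seroma and staining.
- **Collection rule.** Section 8.6 opens with "As the tracers in this trial are used in standard practice no adverse events will be collected for the trial". It then says that seroma, staining and any further reactions to the tracers are to be recorded as outcomes, not as adverse events.
- **Assessments.** In section 7.7 the 2-week item is "Record adverse skin reactions i.e seroma formation and cutaneous staining" and the follow-up call item is "Record self-reported skin reactions". The baseline list includes the time from ICG injection to the end of node excision, but nothing on reactions to the injection.
- **Schedule.** Appendix 4 has one relevant row, "Record seroma formation and cutaneous staining", marked at the 2-week visit and the 3-month call. Day 1 has no entry of this kind.
- **Analysis.** Section 9.2.3 codes the reactions with MedDRA, tabulates them by preferred term and system organ class, and compares rates between groups.

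**The concern.** The outcome is defined and has a planned comparison, but the data-collection sections do not carry it through. Under section 8.1, radiocolloid is given 2 hours before surgery and the other tracers are given around the operation. An acute reaction to a tracer would be expected close to injection. That is a clinical inference, since the protocol does not state onset times. On that inference, the period that matters most for the third component of the outcome is the one with no scheduled entry.

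The subject is not incidental to the trial's rationale. Section 2 says "Abolition of blue dye with its associated risk of anaphylactic reaction (1-3%), skin tattooing and non-licensed use will be notable benefits of ICG". A pilot meant to inform a larger trial should be able to report whether such a reaction occurred, and on the same footing in both arms. As written, two sites could each follow the text and record different things. The operating team knows the allocation, because section 7.4 blinds only pathology and laboratory staff. Without a yes/no field, a blank cannot be told from no reaction.

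An analysis plan cannot repair this, because it concerns what is collected.

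**Working it through.** The protocol states no figure for this outcome, so there is none to reproduce. The check has two parts.

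**1. Setting the sections side by side**

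| Component of the outcome (3.6) | Day of surgery | 2 weeks | 3 months |
|---|---|---|---|
| Seroma | no item | 7.7, Appendix 4 | Appendix 4 |
| Cutaneous staining | no item | 7.7, Appendix 4 | Appendix 4; 7.7 as self-reported skin reactions |
| Other tracer reactions | no item | no item | no item, unless the reaction is a skin reaction the patient reports |

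The 2-week wording in 7.7 introduces seroma and staining with an i.e., so it reads as a definition of what is recorded and not as a list of examples. Section 8.6 covers the third row in principle but gives no time, form or responsible person.

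**2. What is at stake numerically**

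Inputs:
- anaphylaxis risk with blue dye, p = 1% to 3% (section 2);
- patients receiving blue dye, n = 25 (section 4: 100 randomised, 25 in each of four groups, one of which receives blue dye; 4 × 25 = 100 is consistent).

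Expected events, n × p:
- 25 × 0.01 = 0.25
- 25 × 0.02 = 0.50
- 25 × 0.03 = 0.75

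Chance of at least one event, 1 − (1 − p)^25:
- p = 1%: 1 − 0.99^25 = 0.222
- p = 2%: 1 − 0.98^25 = 0.397
- p = 3%: 1 − 0.97^25 = 0.533

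Precision with complete capture, if no event is seen in 25: the one-sided 95% upper bound is 1 − 0.05^(1/25) = 0.113, or about 11%.

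So at least one reaction in the blue-dye arm is plausible. Even with complete recording, a count of zero would not exclude a rate well above the 3% that the protocol quotes.

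**The case against.** A reader might infer that intra-operative allergy will be missed, and that the comparison will show close to zero reactions in both arms. The documents do not support that. The opening sentence of 8.6 is not a refusal to collect tracer reactions: the text after it moves them from adverse-event reporting to outcomes and sets no time limit. A timepoint of evaluation is also not an onset window. Section 10.1 makes the medical notes source data, so a reaction noted in theatre could be entered at the 2-week evaluation. Nor is Appendix 4 exhaustive: it has no row for nodal histology, operating time or tracer use, all of which other sections put on the CRF. The CRF itself is not shown. All of this stands, and it limits the conclusion to capture that is not assured.

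It does not remove the inconsistency. For histology, operating time and tracer use, another section names the CRF as the place of record. For other tracer reactions, no section names a form, and the only times given are the two late ones.

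It is also fair that anaphylaxis is one of several benefits named in section 2, that only one of four groups receives blue dye, and that the trial is an exploratory pilot. The chance of no event in that arm is 0.97^25 = 47% at a 3% risk and 0.99^25 = 78% at 1%. The arithmetic therefore argues for recording the event properly, not for expecting an informative comparison.

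A reader might also connect this with section 9.5, where "no sensitivity analysis accounting for missing data will be performed". The reason given there, that nodes are taken at surgery, does not extend to a later visit or call. But section 9.2 leaves missing-data handling to the analysis plan, which is not shown, so nothing is claimed here on that score.

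**Conclusion.** The point holds as an inconsistency within the protocol. Sections 3.6, 8.6 and 9.2.3 treat other tracer reactions as an outcome to be recorded and compared. The timepoints in 3.6 and the item lists in 7.7 and Appendix 4 do not provide for them, and provide for nothing on the day of injection. Capture is intended but is neither assured nor sure to be uniform across the two sites and the arms.

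Its size is modest: 0.25 to 0.75 expected anaphylactic reactions among 25 blue-dye patients, and a 22% to 53% chance of at least one. This rests on the protocol's 1-3% risk, on full recruitment of that arm, and on independence between patients. That such reactions would arise near injection is a clinical assumption. The figures count reactions that might occur, not reactions that would be lost. The primary outcome is unaffected. The point is worth settling before recruitment because it is cheap to correct then and hard to correct evenly afterwards.

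**What to change.** Reconcile the four places that govern collection.

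- **Section 3.6:** add the day of surgery as an evaluation timepoint for tracer reactions.
- **Section 7.7 and Appendix 4:** add a day-of-surgery item, tracer reaction (yes/no, type), completed from the operative and anaesthetic record. Add other adverse reaction to tracer to the 2-week and 3-month items.
- **Section 8.6:** keep the decision to treat these reactions as outcomes, but state that they are recorded at all three times and on which form.

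The comparison in 9.2.3 can then stand as written, with an explicit yes or no for every patient. The cost is a few CRF fields filled from records that already exist, with no extra visit and no change to treatment. The change makes recording complete and even between arms. It will not make the pilot able to estimate the allergy rate with useful precision, and the report should say so.

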## 8.7. Responsibilities

Chief Investigator (CI) / delegate or independent clinical reviewer:

- Clinical oversight of the safety of patients participating in the trial, including an ongoing review of the risk / benefit.

## 9. STATISTICS AND DATA ANALYSIS

### 9.1. Sample size calculation

This is a pilot study to investigate the sensitivity of ICG alone as a tracer for visualisation of SLNs. A sample size of 100 is based on the number of cases of SLN biopsy undertaken at the two clinical sites on an annual basis. It is expected that randomisation of 100 patients over a 12/18 month period will collect sufficient data to inform the clinically significant difference and estimated sample size for a larger, multicentre, UK wide randomised controlled trial.

### 9.2. Statistical analysis plan

A statistical analysis plan will be prepared for analysis of primary and secondary outcomes and will include a plan for handling missing data.

#### 9.2.1. Summary of baseline data and flow of patients

**No adjustment for baseline characteristics will be required**

#### 9.2.2. Primary outcome analysis

The primary analysis will be performed on the Intention to treat population, for each cohort (Cambridge/ Dundee) separately. As this is not a hypothesis generating trial, all analysis will be exploratory.

Within each group, the number of SLNs for each patient will be recorded numerically in the following categories:

	Study Arm	
Number of SLNs	ICG plus radioisotope or blue dye (standard care)	ICG alone (intervention)
Fluorescence only		
Radioisotope plus fluorescence		
Radioisotope only		
Blue dye plus fluorescence		
Blue dye only		

Pathological exam metastases		
------------------------------	--	--

The proportion of patients within each designated category will be recorded and nodes found on pathological examination to contain metastases documented. Comparison is performed on a procedural basis (proportion of patients with a positive node) using logistic regression with patient positive yes/no.

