### 3.1. Primary objective

To determine the sensitivity of ICG fluorescence imaging alone for SLN detection compared to a combination of ICG and standard tracer.

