### 3.2. Secondary objectives

To determine procedural and node specific positivity rates for intervention and standard care.

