### **9.2.3. Secondary outcome analysis**

The proportion of nodes within each designated category will be recorded and nodes found on pathological examination to contain metastases documented. Comparison is performed on a nodal basis using logistic regression with node positive yes/no. Patient will be used as a random factor in the logistic regression.

ARs will be coded with Medical Dictionary for Regulatory Authorities (MedRA). ARs will be tabulated by Preferred Term and System Organ Class separately and rates of ARs compared between groups.

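### The comparison under 'Primary outcome analysis' uses node positivity, the secondary endpoint; no between-arm comparison of the declared primary endpoint, SLN identification, is stated

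*Protocol*

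**What the plan says.** Section 3.1 of the protocol gives the primary objective as "To determine the sensitivity of ICG fluorescence imaging alone for SLN detection compared to a combination of ICG and standard tracer". The outcome attached to it in section 3.6, repeated in the trial summary, is "Percentage of patients with successful identification of the SLN using ICG alone or combined with a standard tracer, stratified by cohort".

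The secondary objective in section 3.2 is "To determine procedural and node specific positivity rates for intervention and standard care". Section 3.6 defines the procedural version as "Proportion of SLN biopsy cases with tumour deposits in at least one node", counting macrometastases, micrometastases and isolated tumour cells.

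Section 9.2.2, the primary outcome analysis, is done on the intention-to-treat population and separately for each cohort. It provides a table of SLN counts by tracer category and arm, and then says: "The proportion of patients within each designated category will be recorded and nodes found on pathological examination to contain metastases documented". The one comparison it names is: "Comparison is performed on a procedural basis (proportion of patients with a positive node) using logistic regression with patient positive yes/no". Section 9.2.3, the secondary outcome analysis, gives the node-level counterpart: "Comparison is performed on a nodal basis using logistic regression with node positive yes/no", with patient as a random factor.

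**The concern.** The outcome modelled under the primary heading is not the outcome declared primary. Whether a tracer finds a sentinel node and whether the node contains tumour are different questions. The second depends mainly on how many women have nodal disease. It is also loosely tied to tracer failure: Appendix 1 says that when ICG shows no SLN the surgeon samples axillary nodes, so a positive node may still be retrieved from a patient in whom the tracer failed.

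Section 9.1 says the pilot is meant to inform the clinically significant difference and the sample size for a larger trial. Followed as written, its primary comparison would supply an estimate for metastasis and none for identification.

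**Working it through.** This is mainly a check of definitions against analyses. Arithmetic is needed to settle what 'positive' means and to choose a workable method.

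**1. The plan's own figure.** Section 4: 2 cohorts × 2 arms × 25 = 100. This reproduces. Section 9.1 bases it on annual case numbers and gives no alpha, power, effect or margin, so there is no power calculation to check.

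**2. Endpoints and analyses side by side.**

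| Declared quantity | Status in 3.2 and 3.6 | Between-arm comparison stated |
|---|---|---|
| Patient has an SLN identified | Primary | None |
| Patient has a node with tumour | Secondary (procedural) | Logistic regression, 9.2.2 |
| Node contains tumour | Secondary (node specific) | Logistic regression with random patient factor, 9.2.3 |

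The two regressions correspond to the two halves of the secondary objective.

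**3. Does 'positive' mean metastatic or tracer-positive?** Section 9.2.2 does not define it. Three things point to metastatic.
- The sentence just before it is about metastases on pathology.
- Sections 3.2 and 3.6 use procedural positivity for the tumour-deposit outcome.
- Section 9.3 expects 7 to 10 node-positive cases among 50: 7/50 = 14% and 10/50 = 20%. In an arm of 25 that is 25 × 0.14 = 3.5 to 25 × 0.20 = 5 patients. Section 1 cites identification of 98.7% for ICG alone and 96.7% for radiocolloid, which is 25 × 0.967 = 24.2 to 25 × 0.987 = 24.7 patients. Section 9's node-positive rate cannot be an identification rate.

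**4. What is described about identification.** The 9.2.2 table has rows for each tracer and tracer combination, and one for metastases. It has no row for a patient in whom no SLN was identified. Proportions per category are recorded; no comparison is attached to them.

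**5. Would the same regression work with identification as the outcome?** Assume the cited rates apply here. The chance of no failures in an arm of 25 is p^25:
- p = 0.967: 0.967^25 = 0.43
- p = 0.987: 0.987^25 = 0.72

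The chance that at least one of two arms in a cohort has no failures is 1 − (1 − p^25)²: 0.68 if both arms are at 96.7%, and 0.92 if both are at 98.7%. In that event ordinary logistic regression gives no finite odds ratio. An exact interval still works: for 25/25 the two-sided 95% lower limit is 0.025^(1/25) = 0.863, so 86.3% to 100%.

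**The case against.** **The trial is an exploratory pilot.** It is sized on feasibility, section 9.2.2 calls all analysis exploratory, and section 9.3 says the study is not powered. This stands to the extent that no error rate or power claim is damaged. It does not make a comparison of metastasis an answer to a question about identification.

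**A statistical analysis plan is promised in 9.2 and could add the comparison.** It could. But the protocol does not leave this open: it fixes the variable under its primary heading. A later plan must either inherit the mismatch or depart from the protocol.

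**'Positive' might mean tracer-positive.** It is undefined in 9.2.2, so the reading is possible, but step 3 of the working makes it weak.

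**Identification is not ignored.** This stands. SLN counts per patient and category proportions are shown by arm, and a patient with zeros throughout could be recognised as a failure. A reader might infer that the trial will report nothing on identification; the table in 9.2.2 does not support that. What is missing is a stated comparison and an explicit failure category.

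**The wording differs between 3.6 and 9.2.2.** It does; the two match in meaning and are not identical text.

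**The term 'sensitivity' in 3.1 is loose, but 3.6 already attaches the identification percentage to it.** This stands. A reader might infer that the primary objective cannot be estimated because the ICG-alone arm has no second tracer to reveal missed nodes. That applies to sensitivity in the strict sense, and not to the endpoint declared, so rewording 3.1 is optional.

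**Conclusion.** The point holds as a mismatch between endpoint and analysis. The only between-arm comparison in the primary outcome analysis is, in substance, the secondary endpoint, and none is stated for the primary one. The planned primary comparison therefore neither addresses the primary objective nor informs the larger trial on identification.

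The size of the mismatch is the gap between two quantities: 14% to 20% positivity expected by the protocol, against cited identification of 96.7% to 98.7%. The conclusion rests on reading 'positive' as metastatic, which sections 3.2, 3.6 and 9.3 support. The 43% to 72% chance of a failure-free arm rests on the further assumption that the cited rates apply in this trial.

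A reader might go further and infer that the declared endpoint would have good power where positivity has almost none. The documents do not support relying on that. With an assumed 98.7% against 80%, two-sided 5% Fisher power for identification is 84% at 50 per arm. But that needs the cohorts pooled, whereas 9.2.2 analyses them separately. At 25 per arm it is 33%, and for 98.7% against 90% it is 2.6%. Nothing in the protocol supports 80% for ICG alone: section 1 cites over 90% and 98.7%, the latter being the sole-tracer rate and not a rate for the combination. The case for change is that the wrong variable is compared, not that power is lost.

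**What to change.** 1. In 9.2.2, make the primary comparison 'at least one SLN identified by the allocated tracer(s), yes/no', by allocated arm within each cohort. Report a difference in proportions with an exact or score-type confidence interval; exact or penalised logistic regression is an alternative.
2. Add a 'no SLN identified' row to the 9.2.2 table.
3. Move the patient-level metastasis regression to 9.2.3, beside the node-level one.
4. Optionally, change 'sensitivity' in 3.1 to 'SLN identification rate'. Per-node ICG sensitivity relative to the second tracer can then be reported descriptively from the standard-care arm only: fluorescent nodes among those that are hot or blue, which the existing table already counts.

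The cost is wording in 9.2.2 and 9.2.3 (and 3.1 if chosen) and one table row. The sample size stays at 100 and no additional patients are needed. Identification by patient follows from the SLN counts already recorded, provided that failures are entered explicitly.
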